6.3 Concomitant Therapy

Prior to week 12, lipid-regulating concomitant medications should not be altered, unless there is a clinically compelling reason for change. The investigator must contact the Amgen medical monitor to discuss such cases on an individual basis. After week 12, investigators may prescribe any concomitant medications or treatments deemed necessary to provide adequate supportive care except for those listed in [Section 6.4](#). If needed, apheresis will be permitted at any time during the study.

[figure not shown]
6.4 Excluded Treatments During Study Period

The use of antacids is not recommended within the period of two hours before and two hours after dosing with statins.

7. STUDY PROCEDURES

This will be a multicenter, open-label study to assess the long-term safety, tolerability, and efficacy of AMG 145. For the purpose of this study, a month is defined as 4 weeks and a quarter is defined as 12 weeks.

Subjects that fall within a 1 month window of completing a qualifying parent study do not require screening procedures to be performed; they may be enrolled into the study directly, as outlined in [Section 7.1.2](#). All other subjects must go through the study screening procedures as outlines in [Section 7.1.1](#).

Written informed consent must be obtained and will be implemented before protocol specific procedures are carried out. The risks and benefits of participating in the study will be verbally explained to each potential subject prior to entering into the study. The procedures to be performed at each clinic visit are described below and are summarized in [Appendix A](#). Subjects must be fasting for ≥ 9 hours before each study visit where labs are collected. IP should not be administered until all study procedures are completed at each visit. Blood draws for subjects on apheresis (main study and sub-study) will need to occur both before and after apheresis

7.1 General Study Procedures

7.1.1 Screening (for all Non-parent Study Subjects and for Parent Study Rollover Subjects That Have not Completed a Parent Study (EOS/Day 1 Visit) Within the 1 Month Allowable Window)

Subjects who are considered for entry into the study and have the risk and benefits of participating in the study explained will enter screening by signing and dating the informed consent form for this study.

Screening should be completed and the subject randomized or screen failed within 6 weeks of signing the informed consent. The following data will be obtained and procedures performed during screening:

- Written informed consent
- Medical history
- Vital signs (see [Section 7.1.3.1](#)): sitting BP, heart rate (HR)
- Body weight
- Physical exam
- Review for AEs/**adverse device effects (ADEs)**/SAEs (AEs possibly related to study procedures and SAEs are collected during screening)
- Concomitant medication
- 12-lead ECG in triplicate using centralized ECG services equipment
- Blood draw for fasting lipids (≥ 9 hour fasting sample), ApoA1, ApoB, Lp(a), chemistry, coagulation, hematology, PK (PCSK9 only), HbA1c, serum pregnancy (females of childbearing potential only) urinalysis, and FSH (only if required to ensure menopause in a female subject [see [exclusion criterion 4.2.18](#)]) by central laboratory (*Note: eGFR will be calculated by the central laboratory and will be provided to the site for eligibility determination*)

In addition, apheresis subjects will have 2 mandatory screening visits (week -2 and week -1). Week -2 will need to occur on an apheresis day in order to obtain baseline lab values (lipids and PCSK9) prior to study entry. Assessments for week -2 can be found above in [Section 7.1.1](#). Serum pregnancy testing and FSH need not be performed for apheresis subjects at week -2. Assessments for week -1 can be found below in [Section 7.1.2.3](#). All other screening procedures may occur at any time during the 6 week screening window.

If a fasting sample could not be obtained at the initial screening visit and the other screening laboratory assessments confirm eligibility for the study, a fasting lipid sample to determine eligibility must be obtained before the planned day 1 visit.

7.1.1.1 Retesting

If, in the investigator's judgment, lab abnormalities are likely to be transient (ie, subject participated in vigorous exercise and CK is elevated immediately afterwards), laboratory tests can be retested. Triglycerides, CK, liver function, and other laboratory values can be retested during screening as long as the subject can be evaluated for eligibility and randomized within the allowed screening period. Care should be taken to avoid potential inadvertent unblinding of subjects that have completed a blinded (or blinded portion) parent AMG 145 study. In such cases certain laboratory results such as the lipid panel, hs-CRP, and vitamin E may need to be avoided. Further clarification is provided in [Sections 7.1.3.3 and 7.1.3.4](#).

7.1.1.2 Rescreening

Subjects who, in the opinion of the investigator, require major medication changes (ie, statin up-titration, uptitration of blood pressure medications) can be put on a higher dose of medication and rescreened after at least 1 month.

Suitable subjects who are ineligible at the initial screening for other reasons can be re-consented and rescreened at a later time unless they withdraw from screening. There will be a maximum of 2 rescreens per subject.

Rescreened subjects who are re-consented will repeat all screening procedures.

Rescreened subjects will maintain the originally assigned subject identification number.

7.1.1.3 Screen Fail

Subjects who fail any of the eligibility criteria during screening or rescreening need to be screen failed in IVRS before they can be re-consented and re-registered in IVRS for rescreening.

7.1.2 Enrollment (EOS Parent/Day 1 OL)

Day 1 for this open-label (OL) study and the end of study visit for the parent study should occur on the same day. All efforts should be made to minimize any time gaps between the parent study EOS and Day 1 in the OL study. The Day 1 OL visit will need to occur within 1 month of the parent EOS or the subject will need to undergo screening procedures ([Section 7.1.1](#)) prior to enrollment. The following procedures will be performed during the end of study (EOS) visit in the parent study and at the Day 1 visit for all subjects that completed screening procedures:

- Vital signs: sitting blood pressure (BP), heart rate (HR)
- AEs/ ADEs/SAEs

- Concomitant medications
- Physical exam for subjects that did not undergo screening
- Body weight for subjects that did not undergo screening
- Measurement of height, weight, and Tanner stage for adolescent subjects (see the [study glossary](#) for definition of adolescence and [Appendix E](#) for guidance on Tanner staging). If Tanner staging cannot be performed on Study Day 1, it should be performed along with height and weight at the next scheduled study visit.
- Documentation of historical assessments of height, weight and Tanner stage for adolescent subjects (see the [study glossary](#) for definition of adolescence and [Appendix E](#) for guidance on Tanner staging). If documentation of historical assessments cannot be obtained on Study Day 1, it should be done as soon as possible after enrollment
- 12-lead electrocardiogram (ECG) in triplicate using centralized ECG services equipment for subjects that did not undergo screening
- Blood draw for serum pregnancy (females of childbearing potential only) and FSH (for applicable subjects)
- Urinalysis
- Blood draw for fasting lipids (≥ 9 hour fasting sample), ApoA1, ApoB, chemistry, coagulation, hematology, PK (AMG 145; PCSK9), hsCRP, Lp(a), biomarkers, and anti-AMG 145 antibodies
- IP administration

Day 1 - subjects will have the risks and benefits of participating in this study explained to them. Subjects that meet inclusion/exclusion criteria will need to sign a new OLE informed consent form, if they already have not done so, before AMG 145 study drug is administered at the site.

Below are additional analytes, not collected during the parent study's EOS visit that will need to be collected for all subjects at Day 1:

- Fasting Vitamin E
- HbA1c

7.1.2.1 Weeks 2 and 10 (± 7 Days) Non-parent Subjects Only – Mandatory for All Apheresis Subjects, Optional for Non-apheresis Subjects

- Vital signs: sitting blood pressure (BP), heart rate (HR)
- AEs/ADEs/SAEs
- Concomitant medications
- Blood draw for fasting lipids (≥ 9 hour fasting sample), ApoA1, ApoB, Lp(a), PK (AMG 145) and PCSK9
- Administer IP to subjects (as applicable for Q2W subjects)

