Non Amgen Investigational Product Dosage and Administration: Only AMG 145 will be provided for this study.

Control Group: No control group will be used in this open-label study.

Procedures

This will be a multicenter, open-label study to assess the long-term safety, tolerability, and efficacy of AMG 145. For the purpose of this study, a month is defined as 4 weeks and a quarter is defined as 12 weeks.

Subjects that fall within a 1 month window of completing a qualifying parent study do not require screening procedures; they may be enrolled into the study directly, as outlined in [Section 7.1.2](#). All other subjects must go through the study screening procedures as outlines in [Section 7.1.1](#).

Vital signs, **adverse events (AEs)/adverse device effects (ADEs)/serious adverse events (SAEs)**, and concomitant therapy will be evaluated and dietary instruction provided at every study visit, including screening. Other assessments and procedures include fasting lipids, physical exam, measuring body height and weight, assessment of growth and pubertal development (Tanner staging) for adolescent subjects only, 12-lead ECGs, other laboratory assessments, including assessment for anti-AMG 145 antibodies, biomarker sample collection, serum pregnancy testing (females of childbearing potential), urinalysis, and SC IP administration. If the subject consented to pharmacogenetics analyses, deoxyribonucleic acid (DNA) will be extracted from some of their existing blood samples. IP administration by SC injection will be done after all other procedures have been completed. This study includes adjudication of deaths and specific cardiovascular (CV) events by an independent Clinical Events Committee (CEC).

Statistical Considerations

Statistical analyses in this open label, multicenter single arm study will be descriptive in nature. No statistical inference is planned.

Subject disposition, demographics and baseline characteristics will be summarized.

Summary statistics for continuous variables will include the number of subjects, mean, median, standard deviation or standard error, minimum, and maximum. For categorical variables, the frequency and percentage will be given.

Subjects will be summarized according to whether subject rolled over from a parent study and their treatment allocation from a parent study when applicable.

For efficacy analyses, the baseline value is defined as:

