4.2 Exclusion Criteria

All subjects will be ineligible for the study if they fulfill any of the following criteria:

- 4.2.1 Female subject who has either (1) not used an acceptable method(s) of birth control for at least 1 month prior to screening or (2) is not willing to use such a method during treatment with AMG 145 (IP) and for an additional 15 weeks after the end of treatment with AMG 145 (IP) unless subject is sterilized or postmenopausal;
- Menopause is defined as 12 months of spontaneous and continuous amenorrhea in a female \geq 55 years old or 12 months of spontaneous and continuous amenorrhea with a follicle-stimulating hormone level $>$ 40 IU/L (or according to the definition of "postmenopausal range" for the laboratory involved) in a female $<$ 55 years old unless the subject has undergone bilateral oophorectomy
 - Acceptable methods of preventing pregnancy include sexual abstinence, surgical contraceptive methods (vasectomy or bilateral tubal ligation), use of hormonal birth control methods (pills, shots, implants or patches), intrauterine devices (IUDs), or two (2) barrier methods (each partner must use one barrier method) with spermicide – males must use a condom with spermicide; females must choose either a Diaphragm with spermicide, OR or Cervical cap with spermicide, OR Contraceptive sponge with spermicide.
- 4.2.2 Subject is pregnant or breastfeeding, or planning to become pregnant or breastfeed during treatment with AMG 145 (IP) and for an additional 15 weeks after the end of treatment with AMG 145 (IP)
- 4.2.3 Unreliability as a study participant based on the investigator's (or designee's) knowledge of the subject (eg, inability or unwillingness to adhere to the protocol)
- 4.2.4 Experienced a treatment related serious adverse event that led to IP discontinuation in the AMG 145 parent protocol
- 4.2.5 Disorder that would interfere with understanding and giving informed consent or compliance with protocol requirements
- 4.2.6 Have an unstable medical condition, in the judgment of the investigator.
- 4.2.7 Currently enrolled in another investigational device or drug study, or less than 30 days since ending another investigational device or drug study(s), or receiving other investigational agent(s).

In addition, all subjects that undergo screening procedures will be ineligible for the study if they fulfill any of the following criteria:

- 4.2.8 Use of Mipomersen or Lomitapide within 5 months of screening

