6.1.1 Dosage, Administration, and Schedule

All investigational product (IP) will be administered at the investigator site by a qualified staff member during site visits or at home or other location by subjects (or designee, which may include a qualified health care professional) between on-site visits. The date, time, and volume of AMG 145 will be collected and recorded on the individual subject's eCRF for doses administered at the study site. IP administration by SC injection at each on-site visit must be done after vital signs, ECG, and blood draw procedures, if applicable.

IP will be administered either at 6 mL via vials and syringes or, depending on device availability at sites; at 3ml via 3 prefilled autoinjectors/pens or at 3.5 ml via 1 personal injector. The 6 mL dose can be split (eg, 3 injections at 2 mL each) and administered into different injection sites. The SC injections should be administered in a consecutive

fashion with all injections completed within 30 minutes. For further details regarding the injection procedures, the IPIM should be consulted.

Parent Study 20110233 Subjects:

Subjects coming from parent study 20110233 will initiate this study with 420 mg SC monthly (QM) dosing. After 12 weeks of 420 mg SC QM, if observed LDL-C reduction is > 5% and PCSK9 levels have been shown to be maximally suppressed (ie, < 100 ng/mL), subjects may continue QM dosing for the duration of the study. In subjects with PCSK9 levels > 100 ng/mL assessed at the end of a 420 mg SC QM dosing interval (eg, assessed at weeks 4 and/or 8), dosing may be changed to 420 mg SC Q2W at the week 12 visit. If the observed LDL-C reduction from baseline is < 5% and PCSK9 levels have been shown to be maximally suppressed (ie, < 100 ng/mL) the subject may be withdrawn from the study at week 12. Depending on the subject response to 420 mg SC Q2W dosing, these subjects may continue Q2W dosing, return to QM dosing, or be withdrawn from the study at the week 24 visit.

Apheresis Subjects:

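### Non-apheresis women of childbearing potential who roll over directly can receive the first open-label dose before any pregnancy result from this study is known

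*Protocol*

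**What the plan says.** **Entry.** Protocol section 7 states: "Subjects that fall within a 1 month window of completing a qualifying parent study do not require screening procedures to be performed". Section 7.1.2 then sets the default timing: "Day 1 for this open-label (OL) study and the end of study visit for the parent study should occur on the same day". Its list for that visit includes "Blood draw for serum pregnancy (females of childbearing potential only) and FSH (for applicable subjects" and, as a separate item, administration of IP. The rollover table in Appendix A marks both in the Day 1 column.

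**Order at the visit.** Section 6.1.1: "IP administration by SC injection at each on-site visit must be done after vital signs, ECG, and blood draw procedures". The synopsis (Procedures) and section 7 are broader: "IP administration by SC injection will be done after all other procedures have been completed" and "IP should not be administered until all study procedures are completed at each visit".

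**Laboratory.** Section 7.1.3.4 sends on-study samples to the central laboratory, and Table 3 lists serum hCG among the analytes. Section 6.1.3 asks sites to review each visit's central report promptly once it arrives and before the next IP dose.

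**Eligibility.** Exclusion 4.2.2, which applies to all subjects, reads in part "Subject is pregnant or breastfeeding, or planning to become pregnant or breastfeed during treatment with AMG 145 (IP". The Day 1 paragraph of 7.1.2 adds: "Subjects that meet inclusion/exclusion criteria will need to sign a new OLE informed consent form".

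**The concern.** The protocol treats pregnancy as a reason not to give AMG 145. It excludes pregnant women, requires contraception until 15 weeks after treatment ends (4.2.1) and requires pregnancies to be reported over the same 15 weeks after the last dose (9.3). One would expect a result to be in hand before the first dose of this study. For women who roll over directly, the only pregnancy sample this study schedules before dosing is the one taken at the dosing visit itself, and nothing ties the dose to its result.

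What is at stake depends on the parent-study arm. SAP 10.1 shows that 20110233 had a placebo group. For a woman from that group, Day 1 could be a first fetal exposure that a simple test would have avoided. For a woman already on AMG 145 it adds one dose to an existing exposure. This is a point about patient safety; it does not affect any estimate or analysis.

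**Working it through.** No sample size, power or rate is involved, so the check is a comparison of the relevant sections.

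**1. Is there an earlier scheduled test in this study?**

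| Group | Serum pregnancy sample before Day 1 | Source |
|---|---|---|
| Screened subjects, including rollovers outside the 1-month window | Yes, at screening | 7.1.1; Appendix A |
| Apheresis subjects | Yes, at week -1 | 7.1.2.3; the schema note applies week -1 to all apheresis subjects |
| Non-apheresis direct rollovers | None | 7; Appendix A, rollover footnote a |

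**2. What happens on Day 1 for the third group?** On the default same-day path the sequence is: draw the sample, give the first open-label dose, send the sample to the central laboratory, review the report before the *next* dose. Every step complies with 6.1.1, 7.1.2, 7.1.3.4 and 6.1.3.

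**3. Does any other text require the result first?**

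- *Completion of procedures before IP (synopsis, section 7).* The same Day 1 list contains PK, PCSK9 and anti-drug antibody samples, which 7.1.3.4 has shipped onward for assay. If a procedure counted as complete only when its result was known, same-day dosing would be unworkable. The rule can only govern collection.
- *Exclusion 4.2.2.* It bars a woman known to be pregnant. It names no test, result or timing, so it does not detect an unrecognised pregnancy.
- *Exclusion 4.2.1.* Its look-back on contraception runs from screening, a visit this group does not have, and it names no test.
- *The eligibility wording in 7.1.2.* It refers to the criteria in general and adds no verification step.
- *Appendix A, rollover table.* The Day 1 pregnancy cell carries only footnote i, which concerns FSH. Footnote j places pregnancy testing at screening and every 6 months and leaves extra tests to the investigator's discretion.

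The protocol does state such conditions where it wants them. CK above 5 times ULN must be retested before IP is given (6.1.3.1), and eGFR is returned to the site so that eligibility can be decided (7.1.1).

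**4. How long may the result remain unread?** The outer limit is the next dose. Non-apheresis subjects start on QM dosing (6.1.1), which the glossary defines as 4 weeks with a 7-day window:

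- 4 × 7 = 28 days
- 28 + 7 = 35 days

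This is a ceiling and not an expected delay, because 6.1.3 asks for prompt review. The possible exposure before review is one dose of 420 mg wherever in that interval the report is read.

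**5. How many women?** The documents do not say. Section 2.2.4 gives a planned N of 59 for 20110233 without a sex split, so 59 is an upper bound for that parent study only. Other qualifying parent studies are not counted.

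**The case against.** The strongest reply is that the protocol is silent here and does not give permission. Pregnant women are excluded, Day 1 entry is limited to eligible subjects, and an investigator is free to run a local test. On this view the rule exists and only its method of verification is left open. It is true that a woman known to be pregnant cannot be dosed. But the schedule never requires anyone to look before dosing, and discretion to test is not a requirement to test.

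Second, the parent protocols, the laboratory manual and the central turnaround time are not available. A parent-study test shortly before rollover would close most of the gap in practice. This stands as a limit on the size of the problem. It is also why the fix should accept such a result.

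Third, the contrast with screened women can be overstated. Screening may last up to 6 weeks, so their result can be weeks old, and their Day 1 sample is also drawn at the dosing visit. Quarterly visits likewise combine the draw (every 6 months) with dosing. This is fair, but those women have at least one earlier scheduled sample in this study, and at quarterly visits the exposure is already under way.

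Fourth, the numbers are small, the documents give no fetal-risk data, and the 28 to 35 days adds no further dose. All of this stands and bears on weight. None of it supplies the missing requirement.

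**Conclusion.** The concern holds. For non-apheresis women of childbearing potential who roll over directly and are dosed on the parent end-of-study day, the plan requires a pregnancy sample before the first open-label dose but not a known result. Per case, the consequence is one 420 mg dose given before the result need be seen. Few pregnancies are to be expected, and the documents do not allow their number to be estimated.

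The conclusion assumes that the central result does not come back during the visit, and it takes no account of parent-study testing; neither can be checked from the documents. It does not cover women whose Day 1 follows the parent end-of-study visit after a gap: their sample precedes the dose, and 6.1.3 then calls for review of the report first. The point is a worthwhile, inexpensive safety improvement and has no bearing on the validity of the analysis.

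**What to change.** Add one sentence to 7.1.2, and a matching footnote on the Day 1 pregnancy cell of the rollover table in Appendix A: women of childbearing potential who did not undergo screening must have a negative pregnancy result before the first open-label dose. Accept either a same-day urine or point-of-care hCG test at the site, or a recent parent-study serum result that has already been reported; the amendment should state how recent. Keep the central serum draw as it is.

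The cost is one sentence, one footnote and one simple site test for a small, unstated number of women, with no test needed where a recent parent-study result exists. Same-day rollover is preserved. Section 4 leaves entry open to subjects from future qualifying studies, so the rule would also cover them.
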